1.7 Sample Size Considerations

The study is powered to detect a difference of 4.4% in communication improvement, measured as percent of maximal improvement (% MPR) on the WAB-AQ.² This is based on the smallest difference between VERSE and UC-plus estimated from our pilot studies. We have consulted international aphasia experts who have reported a previous consensus that a 5-point difference on the WAB-AQ² is clinically meaningful improvement in communication. It is important to note this relationship is not linear and will vary based on aphasia severity. We believe the 4.4% change in communication status, which is marginally more conservative than the 5-point difference reported in consensus is reasonable, given this is the difference between the two intensive arms of this trial. The required sample size was estimated under the assumption that the effectiveness hypotheses would be analysed using a longitudinal regression model (generalised estimating equations or linear mixed model), with outcomes measured at three times (at baseline, 12 and 26 weeks months).

A sample of 246 participants (82 per arm) will provide 80% power to detect this difference at a (twosided) significance level of $\alpha = 0.05$, after adjusting for a 20% loss to analysis of (lost to follow-up due to death, dropout and non-adherence).

Our pilot data shows similar effect sizes for differences between the VERSE and UC-plus interventions for discourse measures and communication outcomes. Therefore, we believe that the sample size will provide sufficient power to assess differences in discourse outcomes. Pilot data on quality of life for this population was not available at the trial inception however, we expect to observe larger effects on quality of life than on communication or discourse and therefore expect to have sufficient power to assess difference on quality of life.

1.8 Other Data Collection

During the intervention period, all Usual Care speech therapy is documented in medical notes. The detail of all additional trial related aphasia therapy is documented separately on the electronic Case Report Form (eCRF) as part of the clinical trial. A daily speech therapy log is completed for each trial participant which includes content, duration of session and frequency of sessions. Where usual care sessions with participants have occurred prior to the participant's enrolment in the trial, these sessions are retrospectively collected from the participant's medical record to ensure all therapy provided to the participant enrolment is captured. Deviation from the prescribed therapy such as health related complications, patient withdrawal and death are recorded. At the end of the treatment period, a participant diary is provided to the patient to capture resource utilisation information.

Participants are assessed and questioned about general health to determine if there have been any adverse or Serious Adverse Events during the study period.

The assessment visits (Baseline, Week 12 and Week 26) are completed as a single session. If the participant is unable to complete assessment tasks in a single session, they are completed on the same

day if possible (ie: over a morning and afternoon session). If this is not possible, the assessments take place on consecutive days and a protocol deviation is recorded.

Information relating to resource utilisation is obtained by the blinded assessor from the participant and the participant diary and includes general practitioner (GP) visits, hospital and rehabilitation admissions, outpatient and community service use, medication use for anxiety and depression, speech therapy, use of speech aids and devices, employment status, respite care and informal care as a result of stroke. Where possible, resource utilisation data is verified in medical or other hospital records.

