1.9 Blinding

VERSE is a complex intervention and therefore, it is difficult to blind the participants to receipt of intense treatment or usual care. Similarly, it is not possible to blind the clinician providing therapy to the participant's treatment allocation. Every effort is made to ensure only minimal staff are aware of randomisation allocation, and all outcome assessments are conducted by assessors who are blinded to allocation. In addition, chief investigators and trial statistician are blinded to treatment allocation.

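### SAP Section 1.8 has the blinded outcome assessor ask participants about speech therapy, which is liable to disclose intensive versus usual-care allocation, the primary contrast

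*SAP*

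**What the plan says.** On who asks, and whom, SAP Section 1.8 reads: "Information relating to resource utilisation is obtained by the blinded assessor from the participant and the participant diary". The list of items that follows includes "medication use for anxiety and depression, speech therapy, use of speech aids and devices".

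On blinding, Section 1.9 says that participants are difficult to blind to intense treatment or usual care and that treating clinicians cannot be blinded. It then states that "all outcome assessments are conducted by assessors who are blinded to allocation".

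Four other statements in Section 1.8 bear on the point:

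- The diary: "At the end of the treatment period, a participant diary is provided to the patient to capture resource utilisation information".
- Usual-care therapy: "During the intervention period, all Usual Care speech therapy is documented in medical notes". Trial therapy is recorded separately, on the eCRF, with a daily log for each participant.
- Verification: "Where possible, resource utilisation data is verified in medical or other hospital records". The person who does this is not named.
- The visit: "The assessment visits (Baseline, Week 12 and Week 26) are completed as a single session". The order of tasks within it is not given.

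**The concern.** Neither participants nor therapists can be blinded, so protection against biased scoring rests on the assessor not knowing the arm. The primary outcome is a language test that the assessor administers. The BNT, the discourse sample, the SAQoL-39 and the ADRS belong to the same follow-up assessments.

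The arms differ in the speech therapy they receive, and speech therapy is one of the things the assessor has to ask about. A reply that covers the intervention period would tell the assessor whether the participant was in an intensive arm. If that happens before scoring, knowledge of allocation can influence how the test is given and marked. The presumed direction of any resulting bias is in favour of the intensive arms.

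**Working it through.** This is a question of procedure, so the main check sets the SAP's statements side by side. No sample-size calculation bears on it.

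**1. What an answer could reveal.** Section 1.5 gives both intensive arms 20 extra sessions of 45 to 60 minutes.

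- 20 × 45 / 60 = 15 hours and 20 × 60 / 60 = 20 hours, which reproduces the SAP's own range of 15 to 20 hours on top of usual care.
- The primary test (Sections 3.5.2 and 3.5.4) pools UC-Plus and VERSE against UC. An answer about the intervention period would separate exactly these two groups.
- Section 1.5 matches VERSE to UC-Plus on intensity, so amount of therapy does not separate those two.

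**2. What period the question covers.** The diary begins when treatment ends, so it does not record trial sessions as they happen. However, the participant is named as a source alongside the diary, and no look-back limit is stated. Treatment ends by day 50 and week 12 is day 84: 84 − 50 = 34 days at least. A participant asked about speech therapy may well mention a daily course that finished some weeks before, but the SAP does not establish that this happens.

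**3. Whether it is asked at week 12.** Section 1.8 does not name the visits. Two places point to week 12 as well as week 26. Hypothesis 6 in Section 1.2 claims cost-effectiveness at both times (Section 3.8 names only 26 weeks), and Appendix Table 3 reports total therapy amount at both. For therapy after the intervention period, the participant and diary are the only primary source that Section 1.8 names.

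**4. Which scores are exposed.**

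| Score | Exposed if |
|---|---|
| 12 weeks (primary) | the resource interview comes before scoring at that visit |
| 26 weeks | the interview comes before scoring at that visit; or the question is asked at week 12 and the same assessor returns |

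The SAP neither states nor excludes any of these conditions.

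**5. Sensitivity of the outcome.** From the formula in Section 3.5.1, one AQ point at follow-up equals 100 / (100 − baseline AQ) in %MPR. The AQ shift equal to the 4.4 %MPR target of Section 1.7 is therefore 4.4 × (100 − baseline AQ) / 100. The SAP gives no mean baseline AQ, so one value is assumed in each randomisation stratum. The last column divides by 0.5, assuming that half of intensive-arm participants are disclosed.

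| Assumed baseline AQ | Shift if all disclosed | Shift if half disclosed |
|---|---|---|
| 20 (severe) | 4.4 × 0.80 = 3.52 | 7.04 |
| 50 (moderate) | 4.4 × 0.50 = 2.20 | 4.40 |
| 80 (mild) | 4.4 × 0.20 = 0.88 | 1.76 |

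These are average AQ points of leniency among disclosed participants that would equal the whole target. Nothing in the SAP says that leniency of this size, or disclosure at these rates, occurs. The 4.4 figure comes from a pilot difference between VERSE and UC-Plus and serves here only as a yardstick.

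**The case against.** The strongest reply is that Section 1.8 separates the two streams of data. Trial therapy goes on the eCRF and the daily log, usual-care therapy during the intervention period is in the medical notes, and the diary is handed out only afterwards. On that reading the assessor asks about therapy after the intervention period, and nothing says that this differs by arm. This stands as far as it goes: disclosure is not demonstrated. It does not remove the risk, because the participant is questioned as well as the diary and no look-back limit is set.

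A reader might infer that the 26-week assessor already knows the arm. The SAP does not support this. Section 1.6 speaks of a blinded assessor and Section 1.9 of assessors, and neither says that one person does both visits.

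A reader might also infer that all arm comparisons are affected. Amount of therapy points only to intensive versus usual care.

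Section 1.6 leaves the assessment schedule to the main protocol, which is not at hand. Task order, assessor scripts and a check of blinding may be there, so their absence can be stated only of this SAP. That objection stands. However, a task order alone would not protect week 26 if the same assessor returned after hearing the answer at week 12.

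Finally, Section 3.5.3 already reports 13% of primary-outcome data as missing, so outcome collection was under way. Changes to visit instructions cannot protect visits already done. That is also correct.

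**Conclusion.** The concern holds as a risk written into the stated procedure, and it is more than an omitted detail. Section 1.8 positively assigns the speech-therapy question to the person whose blinding Section 1.9 relies on. Following it as written is liable to disclose intensive versus usual-care allocation, the contrast tested in the primary analysis.

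It would be too strong to say that assessors are unblinded, that the 26-week scores are compromised, or that the trial is not assessor blinded. Those conclusions need facts about look-back, task order and assessor continuity that the SAP does not give.

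The size of any bias cannot be estimated from the document. The AQ conversions (2.2 points at an assumed baseline of 50, 0.88 at 80) show only that modest differences in scoring would matter against a 4.4 %MPR target, most of all in mild aphasia. The change is worth making because it is cheap and lowers the risk of detection bias at visits still to come.

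**What to change.** For remaining visits:

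- Remove the speech-therapy item and the medical-record verification from the blinded assessor's tasks.
- Take intervention-period therapy from the eCRF log and medical notes, where Section 1.8 already places it. Take later therapy from diary pages returned to the site staff who already document therapy.
- Have the assessor collect the other resource items only after the WAB-R AQ, BNT, discourse, SAQoL-39 and ADRS are completed and entered.
- Have the assessor record at each visit whether allocation was disclosed, and report this by arm.

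For visits already done, report the task order used and any known unblinding. If the protocol already sets a task order or a blinding check, cite it in Sections 1.8 and 1.9.

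The cost is a change to the CRF and the visit instructions, with no additional assessor. The downside is that site staff must collect the diary pages, which may need a separate contact when follow-up takes place at the participant's residence.

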1.9 Blinding

VERSE is a complex intervention and therefore, it is difficult to blind the participants to receipt of intense treatment or usual care. Similarly, it is not possible to blind the clinician providing therapy to the participant's treatment allocation. Every effort is made to ensure only minimal staff are aware of randomisation allocation, and all outcome assessments are conducted by assessors who are blinded to allocation. In addition, chief investigators and trial statistician are blinded to treatment allocation.

1.9.1 Unblinding

Only the Data and Safety Monitoring Committee (DSMC) have access to progressive data. The DSMC Chair is [name], University of Sydney, NSW, Australia. The DSMC review unblinded data in accordance with the DSMC Charter (Version 1.0, 25 February 2015).

1.10 Definition of the Outcomes

1.10.1 Primary Outcome

The primary outcome is improvement in communication at 12 weeks after stroke. Communication outcome is measured by the Western Aphasia Battery- Revised Aphasia Quotient (WAB-R (AQ)).² Improvement will be assessed using the percent of maximal potential recovery achieved (%MPR).¹⁹ A formal definition of %MPR¹⁹ is provided in Section 3.5.1.

1.10.2 Secondary Outcome Measures

The secondary outcome measures include effectiveness, quality of life, safety and cost effectiveness measures. These are:

- Communication improvement at 26 weeks, assessed as %MPR¹⁹ at 26 weeks
- Improvement in connected speech at 12 and 26 weeks on discourse measures¹⁰⁻¹⁶
- Quality of life measured by the Stroke and Aphasia Quality of Life (SAQOL)¹⁷ scale
- Depression measured at 12 and 26 weeks by the Aphasia Depression Rating Scale (ADRS)¹⁸
- Adverse Events and serious adverse events as defined in the trial protocol
- Cost effectiveness of VERSE and UC-Plus therapies compared to Usual Ward Care. The economic analysis will be outlined separately in an Economic Analysis Plan

2 Funding

This study is funded by the National Health and Medical Research Council (NHMRC), Australia (Project Grant Number 1044973), The Tavistock Trust for Aphasia, United Kingdom and Edith Cowan University, Australia. The funders of this study have no influence on the study design, data collection, data interpretation, writing of the protocol or statistical analysis plan.

3 Statistical Plan

3.1 Analysis principles and general considerations

- All outcomes and analyses are prospectively characterised as primary or secondary.
- Differences in all endpoints between the three arms of the trial (VERSE, UC-Plus, UC) will be tested independently at the two-tailed 5% significance level. All estimates of treatment effects will be presented with 95% confidence intervals.
- No formal adjustments will be undertaken to constrain the Type I error associated with planned secondary or exploratory analyses. The information provided by analyses is designed to supplement the evidence from the primary analyses; it will provide a more complete characterization of the treatment effects.
- The analyses for all outcome measures (effectiveness, quality of life and safety) will be conducted on an intention the treat (ITT) basis i.e. all patients will be analysed as members of the group to which they were randomised, irrespective of whether they received the allocated treatment or not. The ITT strategy for VERSE is based on the following principles:
 - All available outcome data are collected on all randomised patients.
 - All participants are analysed in the groups to which they are randomised.
 - All available outcome data will be used in the primary analyses. The primary analyses will be reported without missing data imputed.
 - A separate analysis with missing data imputed will also be reported. Missing data will be assumed to be missing at random (see section 3.5.3)
 - A sensitivity analysis including all randomised individuals will be conducted. The sensitivity analysis will consider alternative assumptions about data missing not at random (MNAR) (see section 3.10).
- A per-protocol analysis will be conducted separately, but will not be included in the primary results for this trial. The per-protocol analysis will be described in greater detail when it is published. However, it will be based on the following principles:
 - The per-protocol cohorts will be based on whether or not participants received the planned minimum 15 hours of direct aphasia therapy as the intervention dose.
 - The per-protocol cohort will include:
 - VERSE participants who receive at least 15 hours of direct language therapy over the intervention period;
 - UC-Plus participants who receive at least 15 hours of direct language therapy over the intervention period;
 - All UC participants who are randomised to the UC group.
- For primary and secondary analyses, the treatment effects for the primary effectiveness outcomes will be adjusted for baseline aphasia severity, measured by the WAB-R (AQ)² and baseline stroke severity measured with the NIHSS.⁴ Unadjusted analyses will be reported separately from these pre-specified analyses.

- Subgroup analyses will be carried out irrespective of whether there is a significant treatment effect on the primary outcome. Their purpose is to supplement evidence from the primary analyses to help to fully characterize the treatment effect. Results from subgroup analyses will be interpreted in this context.
- Analyses will primarily be conducted using the R Statistical Programming Language²⁰ and supplemented with SPSS²¹ to generate formatted tables.

3.2 Interim Analysis and Stopping Rules

There are no formal interim analyses planned for this trial. The DSMC periodically reviews data for the primary outcome measure and safety, and will advise the chair of the Executive committee if, in their view, the randomised comparisons have provided both (i) 'proof beyond reasonable doubt' that very early aphasia rehabilitation (VERSE and UC-Plus groups) is clearly indicated or clearly contraindicated because of safety concerns and (ii) evidence that might influence future patient management. The DSMC are guided by Haybittle-Peto boundaries in making this determination. That is, they work on the principle that a difference of at least 3 standard errors in the analysis of effectiveness or serious adverse events (e.g. death from all causes, aspiration pneumonia within the first 50 days post stroke) may be needed to justify halting, or modifying the study before the planned recruitment is completed.

3.3 Trial Profile

The trial will be reported in accordance with the CONSORT statement for non-pharmaceutical trials¹⁹ and the VERSE therapeutic protocol conforms to the SPIRIT statement.^{22,23} The report will include the number of screened patients who met the inclusion criteria, the number included, and the major reasons for exclusion of eligible patients. At follow up, the number of patients withdrawn, lost to follow up and the number who died within that period will be reported.

3.4 Patient Characteristic and baseline comparisons

Baseline participant and stroke characteristics will be presented for each of the three groups: UC, UC-Plus and VERSE (Table 1). These will include: age, gender, geographic region (Australia/NZ), stroke risk factors, stroke type, stroke severity (NIHSS),⁴ mRS,⁵ time to randomisation and baseline assessment. Baseline communication, cognition and swallowing characteristics will be presented in Table 2 and will include Aphasia severity, as measured by the WAB-R (AQ),² clock drawing test, Discourse Scores (words, correct information units),¹¹⁻¹⁶ AuSTOMS,⁸ and RHBOMS.⁷

Discrete variables will be summarized as frequencies and percentages. Unless otherwise indicated in the tables, percentages will be calculated according to the number of patients for whom data are available. If there are more than 5% missing values, the denominator will be indicated in the corresponding summary table. Continuous variables will be summarized by the mean and standard deviation (SD) or by the median and interquartile range (IQR). Durations and time intervals will be summarized by medians and IQRs.

3.5 Primary Outcome: Communication Recovery at 12 weeks by Intensity

3.5.1 Primary Outcome Measure

The primary outcome is improvement in communication at 12 weeks after stroke. Communication outcome will be measured by the WAB-R (AQ).² The WAB-R (AQ) is a comprehensive measure incorporating production of spoken language and auditory comprehension. Improvement will be assessed using the percent of maximal potential recovery achieved (%MPR),¹⁹ which is calculated as the ratio of the difference in WAB-R (AQ)² at 12 weeks and WAB-R (AQ)² at baseline, divided by the difference of maximal attainable score on WAB-R (AQ)² and the WAB-R (AQ)² at baseline. That is,

$$\% MPR \text{ at } 12 \text{ weeks} = \frac{(AQ \text{ at } 12 \text{ weeks}) - (AQ \text{ at } \text{ baseline})}{(\text{Maximum attainable } AQ \text{ score}) - (AQ \text{ at } \text{ baseline})} \text{X}100$$
$$= \frac{(AQ \text{ at } 12 \text{ weeks}) - (AQ \text{ at } \text{ baseline})}{100 - (AQ \text{ at } \text{ baseline})} \text{X}100$$

3.5.2 Statistical Hypothesis

The primary research hypothesis is that:

Compared to usual care alone, providing very early daily aphasia therapy (UC-Plus or VERSE) will result in greater improvements in communication ability at 12 weeks post stroke. This will be tested by refuting the null hypothesis that there is no difference in communication recovery, between the usual care group (UC) and the groups receiving very early intensive therapy (UC-Plus or VERSE) at 12 weeks post stroke. For purpose of testing this intensity hypothesis, the UC-Plus and VERSE groups will be combined into a single high intensity group.

3.5.3 Treatment of Missing Values

The primary analyses will be presented both with and without imputation of missing data. The imputation will treat missing values as missing at random (MAR). i.e. it will be assumed that the missing data are related to observed data, but not related to the value of the missing data itself. That is, it is assumed that the values of the missing data may reasonably be predicted from all observed data. In particular, it will be assumed that missing values of the primary outcome measure (WAB-R $(AQ)^2$ at 3 months) may be estimated from variables on which data has been collected (e.g. baseline aphasia severity, baseline stroke severity, age, gender, lesion size and location), and on the observed values of WAB-R (AQ).² Multiple imputations will be conducted using chained equations.²² A separate model will be developed for each imputation. The pooled result of these imputed models will be reported and compared with the primary model (without imputed data).

Based on monitoring by the DSMC, 13% of the data for the primary outcome measure in the VERSE trial is missing at the time of publication of the statistical analysis plan. This is substantially less than in previous aphasia trials and less than the 20% missing data that had been planned for in the planning of this trial.¹ The assumption that the data are missing at random was discussed by the VERSE Executive Committee as well as the DSMC, and considered to be plausible based on the information available at the time. Sensitivity analyses that consider various other plausible assumptions about missing data will be presented (see below section 3.10, page16).

3.5.4 Analysis Method:

The primary aim of this trial is to test the effect of intensity of therapy in early stroke recovery. This is achieved through the primary effectiveness hypothesis which will be analysed using a linear mixed effects regression model with %MPR¹⁶ as the outcome measure. The UC-Plus and VERSE groups will be combined into a single high intensity group. This combined intervention group will be compared to the UC group on the primary outcome measure (%MPR¹⁶ at 12 weeks). The model will adjust for differences in baseline aphasia severity and baseline stroke severity by including the baseline WAB-R(AQ)² score and the baseline NIHSS⁴ score as covariates in the model. The effect of hospital site will be controlled for by including hospital site as a random effect. The treatment effect will be reported as difference in %MPR with the corresponding 95% confidence interval.

Since publication of the trial protocol¹ five new sites have been added to address low participant recruitment. As a result, the Executive Committee decided there was a need to include hospital site as a random effect. This required the adaptation of our original statistical plan from using General Estimating Equations model (GEE) to a Linear Mixed Effect Regression models.

3.5.5 Subgroup Analyses:

The linear mixed effects regression model will be modified to analyse the difference in the primary effectiveness outcome (%MPR¹⁶ at 12 weeks) between

- 1) the VERSE group and UC group AND
- 2) the UC- Plus group and the UC group

As with the primary analysis, the model will adjust for differences in baseline aphasia severity and baseline stroke by including the baseline WAB- $R(AQ)^2$ score and the baseline NIHSS⁴ score as covariates in the model. The effect of hospital site will be controlled for by including recruiting site as a random effect. The main between-group difference at each time point will be assessed through the interaction effect of group and timepoint. The treatment effect for each subgroup analysis will be reported as difference in %MPR¹⁶ with the corresponding 95% confidence interval.

No corrections for multiple testing in subgroup analyses will be undertaken for these planned analyses. The unadjusted p-values will be reported together with the number of subgroup analyses undertaken.

3.6 Secondary Effectiveness Hypotheses:

The following secondary effectiveness hypotheses will be assessed:

- 1. VERSE (standardised, daily very early) aphasia therapy will result in greater improvements in communication ability than UC-Plus (non-standardised daily very early), as measured by the WAB-R (AQ),² at 12 weeks and 26 weeks post stroke.
- 2. VERSE (standardised, daily very early) aphasia therapy and UC-Plus (non-standardised daily very early) will each result in greater improvements in communication ability than Usual Care alone (UC), as measured by the WAB-R (AQ),² at 12 weeks and 26 weeks post stroke.
- 3. VERSE (standardised, daily very early) aphasia therapy will result in greater improvements in connected speech than UC-Plus (non-standardised daily very early) as measured on Discourse Analysis^{10,11} (number of words, number of Content information units; % Content information units), at 12 weeks and 26 weeks post stroke.
- 4. VERSE (standardised, daily very early) aphasia therapy and UC-Plus (non-standardised daily very early) will each result in greater improvements in connected speech than Usual Care alone (UC), as measured by Discourse Analysis¹⁰⁻¹⁶ (number of words, number of Content information units; % Content information units), at 12 weeks and 26 weeks post stroke.

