1.6 Baseline and follow-up assessments

All stroke patients with aphasia, who are at least 18 years old, are screened for inclusion in the study. Those screened and deemed ineligible for the study are entered onto a screening log which outlines the reason for non-inclusion. Details of the screening and recruitment procedures, as well as the assessment schedule are included in the main trial protocol.

The assessment timeline is outlined in Figure 1. Baseline assessment occurs no earlier than two days from the onset of stroke and no later than 14 days from the onset of stroke. Participants undergo the (AQ) component of the WAB-R.² Participants are also assessed for their medical and stroke history. Baseline data collection includes the collection and documentation of:

- 1) Demographic details including age, gender, past medical history, languages spoken, education level, handedness, employment, Aboriginal or Torres Strait islander status and living arrangements.
- 2) Stroke type and severity (type, hemisphere, first or recurrent stroke, National Institute of Health Stroke Scale, (NIHSS⁴), modified Rankin Scale (mRS⁵), Oxfordshire Community Stroke Project Classification (OCSP⁶), Royal Brisbane Hospital Outcome Measure for Swallowing (RBHOM⁷) and Australian Therapy outcome measures (AusTOMS⁸).
- 3) Additional baseline assessments including the Boston Naming Test (BNT⁹), the "clock drawing" cognitive sub test, and discourse collection.
- 4) Time of assessment and aphasia therapy commencement.

Therapy commences the day after the baseline assessment, and is completed within a maximum of 25 working days and must be completed by day 50 post stroke.

The participants are followed up at their place of residence or in the hospital clinic by a blinded assessor, 12 weeks and 26 weeks after the date of the stroke. Patient assessments at these follow-up visits include:

- the Aphasia Quotient component of the Western Aphasia Battery-Revised²
- the Boston Naming Test,⁹
- Discourse collection,¹⁰⁻¹⁶
- Stroke and Aphasia Quality of life questionnaire 39 item version¹⁷; and
- The Aphasia Depression Rating Scale.¹⁸

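### The primary model leaves out age, which is collected at baseline and which the SAP itself lists as a predictor of the 12-week score; adding it is a small, nearly free gain

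*SAP*

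**What the plan says.** **Analysis model.** The primary comparison (UC-Plus and VERSE combined against UC, %MPR at 12 weeks) uses a linear mixed model. Section 3.5.4 states: "The model will adjust for differences in baseline aphasia severity and baseline stroke severity by including the baseline" AQ and NIHSS scores as covariates. It adds: "The effect of hospital site will be controlled for by including hospital site as a random effect". The general principles in 3.1 fix the same set for primary and secondary analyses: "the treatment effects for the primary effectiveness outcomes will be adjusted for baseline aphasia severity" and for baseline NIHSS, with unadjusted results reported separately. Sections 3.5.5, 3.6.2 and the quality-of-life model in 3.7 repeat AQ, NIHSS and site.

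**Baseline data.** Section 1.6 lists "Demographic details including age, gender, past medical history" among the items collected.

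**Missing data.** Section 3.5.3 says that missing 12-week AQ values "may be estimated from variables on which data has been collected (e.g. baseline aphasia severity, baseline stroke severity, age, gender, lesion size and location"), together with observed AQ values. Section 3.1 makes the un-imputed analysis the primary one. Section 3.5.3 adds a multiple-imputation analysis under missing at random, to be compared with it, and reports 13% of the primary outcome missing so far. Section 3.10 adds a delta-adjusted pattern-mixture analysis.

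**The concern.** The SAP relies on age as a predictor of the 12-week score when it fills in missing values, but not when it estimates the treatment effect. Two modest consequences follow.

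- **Precision.** If age predicts %MPR beyond baseline AQ, NIHSS and site, leaving it out puts that variation in the residual and widens the confidence interval. Randomisation is stratified by aphasia severity only (1.4), so age is not balanced by design.
- **Missing data.** For the 12-week comparison, the un-imputed model needs missingness to be unrelated to outcome given treatment group, AQ, NIHSS and site. The assumption argued for in 3.5.3 also conditions on age and other variables. If age-related loss differs between the compared groups, the headline estimate carries a bias that a model containing age would largely remove.

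**Working it through.** **1. The plan's own figure.** Section 1.7 gives 246 participants (82 per arm), 80% power, two-sided 5%, a difference of 4.4 %MPR and 20% loss. No SD or within-person correlation is given, so 246 cannot be reproduced, only solved backwards.

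- Analysed per arm: 82 × 0.8 = 65.6.
- Standardised effect needed for 80% power: 1.960 + 0.842 = 2.802.
- Implied effective SD: 4.4 / (2.802 × √(2/65.6)) = 9.0.

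The 4.4 refers to VERSE against UC-Plus. The primary comparison pools those two arms against UC (2:1). With the same difference and SD, its variance is 1.5/n instead of 2/n, so the standardised effect is 2.802 × √(4/3) = 3.235 and power is 89.9%.

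**2. Precision gained from age.** Let R² be the share of residual variance that age explains after AQ, NIHSS and site. The SAP gives no value; 2% and 5% are assumptions. The formulas are: SE ratio = √(1 − R²); equivalent extra participants = 246/(1 − R²) − 246; power = Φ(standardised effect/√(1 − R²) − 1.96).

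| Assumed R² | SE ratio | SE falls by | Equivalent extra participants | Power, pairwise (from 80.0%) | Power, pooled 2:1 (from 89.9%) |
|---|---|---|---|---|---|
| 2% | 0.990 | 1.0% | 5 | 80.8% | 90.5% |
| 5% | 0.975 | 2.5% | 13 | 82.0% | 91.3% |

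The pairwise power column starts from the planned 80%, so it does not depend on the SD.

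**3. Exposure to age-related loss.** Take 13% missing (3.5.3).

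- If loss depends on age in the same way in both compared groups, the mean age of those observed shifts equally in each, and the treatment effect in an additive model is unbiased.
- Suppose instead that the odds of being missing double per SD of age in one compared group only (an assumption). With logistic missingness at 13% overall, the mean age of those observed in that group falls by about 0.085 SD. Bias = √R² × residual SD × 0.085.

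| Assumed R² | Residual SD 9.0 (implied in step 1) | Residual SD 20 (assumed) |
|---|---|---|
| 2% | 0.141 × 9.0 × 0.085 = 0.11 %MPR | 0.141 × 20 × 0.085 = 0.24 %MPR |
| 5% | 0.224 × 9.0 × 0.085 = 0.17 %MPR | 0.224 × 20 × 0.085 = 0.38 %MPR |

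Against the 4.4 target this is 2.5% (0.11/4.4) to 8.6% (0.38/4.4). If the differential loss arises in only one of the two pooled intensive arms, the figures roughly halve, to 0.05 to 0.19 %MPR. The SD of 20 is shown because 9.0 is an effective value from a calculation that assumed a longitudinal model (1.7), and the single-visit SD may be larger.

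**The case against.** The strongest reply is that nothing here is inconsistent. Sections 3.1 and 3.5.4 agree on a defensible set: baseline AQ, which underlies the randomisation strata, and stroke severity. An imputation model normally holds more variables than the analysis model, and the list in 3.5.3 is given by way of example. Randomisation makes the comparison valid without age, and the confidence interval already allows for chance imbalance. The imputed analysis and the delta analysis of 3.10 are both planned and probe the missing-data issue. All of this stands, and it is why the point is minor.

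A reader might infer more than the document supports:

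- **That stroke type should be added too.** It is collected (1.6), but 3.5.3 does not name it as a predictor of the 12-week AQ, so the SAP gives no basis for claiming a loss from omitting it.
- **That the imputed and un-imputed results could not be compared cleanly.** The SAP specifies no different covariate set for the analysis model after imputation. A difference between the two would show what the imputation contributes, which is the purpose of the comparison.
- **That the headline estimate is biased.** This needs age-related loss that differs between the compared groups. The SAP reports no missingness by age or arm.

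The reply does not remove the remaining point: the SAP treats age as predictive, the value is already collected, and using it costs almost nothing.

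**Conclusion.** The point holds as a minor, nearly free improvement. The primary analysis is valid as pre-specified and nothing in the SAP is contradicted. The expected gain is a standard error smaller by about 1.0% to 2.5% and about 1 to 2 points of power, if age explains 2% to 5% of the variance left after AQ, NIHSS and site. That range is an assumption; if age adds nothing beyond those variables, the gain is nil. The protection against differential age-related loss is worth roughly 0.1 to 0.4 %MPR under the scenario worked above, and half that if only one intensive arm is affected.

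Two limits apply. Adding age narrows the gap between the two missing-at-random assumptions but does not close it, because gender and lesion size and location stay outside the model. And 3.5.4 does not say whether the primary model is single-visit or longitudinal; if it is longitudinal, observed 26-week values also inform the un-imputed analysis and the gap is already smaller.

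**What to change.** While the trial statistician is still blinded to allocation (1.9), make these changes:

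- In 3.1 and 3.5.4, add age at baseline as a continuous fixed covariate beside baseline AQ and NIHSS. Section 3.1 must change with 3.5.4, because it fixes the covariate set for primary and secondary analyses.
- Make the same change in 3.5.5, throughout 3.6.2, and in the quality-of-life model of 3.7, so that all models use one set.
- Keep the model with AQ, NIHSS and site only as a named supporting analysis, next to the unadjusted one already promised in 3.1.
- State in 3.5.3 that age is definitely in the imputation model, so that the imputation contains every covariate of the analysis model.

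If the team prefers the present set, a sentence in 3.5.4 saying why age is left out of the headline model would be enough. The cost is SAP wording and one degree of freedom per model; no new data are needed.
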